12.3.	AMENDMENTS TO THE PROTOCOL	29
12.4.	DATA RECORDS.....	29
13.	PUBLICATION AND AGREEMENT	29
14.	INVESTIGATORS AGREEMENT	30
15.	REFERENCES	31
16.	APPENDIX A	32
	APPENDIX B	35

Braintree Laboratories, Inc.
Protocol Number BLI400-303

Confidential

CLINICAL PROTOCOL SUMMARY SHEET**STUDY TITLE:**

An Open Label Study of Chronic Use of BLI400 Laxative in Constipated Adults

PROTOCOL: BLI400-303**VERSION DATE:** 4-13-2016**IND NUMBER:** 118,906**OBJECTIVE:**

To evaluate the safety of chronic use of BLI400 Laxative in constipated adults.

STUDY DESIGN:

This is an open-label, multi-center study in constipated outpatients.

SUBJECTS:

Approximately 300 male or female adult subjects with a history of constipation will be enrolled in this study (including approximately 100 elderly subjects).

STUDY MEDICATIONS:

BLI400 Laxative (21 grams of Lactitol Monohydrate, NF)

DURATION OF TREATMENT

Subjects will take BLI400 laxative daily for 12 months (52 weeks). Participation in this study will last for approximately 54 weeks, including the 14 day follow up telephone call.

PRIMARY ENDPOINT

Safety will be analyzed through the use of adverse event and ECG data, and the comparison of chemistry, hematology, and urinalysis values as measured at baseline and at specific time points throughout the study.

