2. STUDY OBJECTIVE

To evaluate the safety of chronic use of BLI400 laxative in constipated adults.

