9.3.2. Safety Analyses

Analysis of safety will be performed using the modified Intent to Treat population (see [Section 9.4](#)).

Adverse Events

Adverse Events will be coded using the MedDRA classification to provide a preferred term and primary system organ class for each event. Proportions of subjects with adverse events will be presented for the overall study population, and each demographic subgroup (age, gender and race). Tables of AEs will be presented by system organ class and preferred term, and include overall totals for AEs within each system organ class. Counting will be done by subject and not by event. A table of counts and percentages will also be made of those subjects with SAEs or AEs which led to withdrawal from the study.

Treatment-emergent AEs are defined as adverse events that had an onset day and time on or after the day and time of the first dose of study drug until the Day 374 Follow-up Call. Adverse Events having missing onset dates will be considered as treatment emergent.

The difference in adverse event rates between study periods will be tested by Chi-Square or Fisher's exact test with 95% confidence intervals.

Laboratory Parameters

Summary statistics (i.e., mean, minimum, maximum, standard deviation, and number of subjects) will be presented for each laboratory parameter at each visit. Laboratory data will be summarized for the overall population and the elderly and non-elderly subgroups. When calculating the summary statistics only, the last observation within a visit window will be used if there are multiple observations. Changes from baseline (Visit 1) will be presented in a similar format. An additional listing will be provided of those subjects who have clinically significant laboratory values. The data will also be presented as shift tables and clinically significant abnormalities will be examined.

Results of laboratory tests for the change from baseline (Visit 1) and group differences will be tested using ANOVA.

Vital Signs

Summary statistics (i.e., mean, minimum, maximum, standard deviation, and number of subjects) will be presented for each vital sign at each visit and compared to the values obtained at Visit 1. When calculating the summary statistics only, the last observation within a visit window will be used if there are multiple observations. The data will also be presented as shift tables and clinically significant abnormalities will be examined.

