ECG variables will be tabulated and presented for data collected at each visit. Data will be tabulated and summarized with descriptive statistics (N, mean, SD, CV%, SEM, minimum, and maximum) for each of the ECG variables. The differences in ECG variables between Visit 1 (Baseline), Visit 2 and Visit 6 will be tested using ANOVA.

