9.3.3. Efficacy Analyses (Patient Reported Outcomes)

Subject constipation symptoms and quality of life indicators will be analyzed using data from the subject-completed PAC-SYM and PAC-QOL instruments. Change from baseline to each visit time point will be presented for each collected measure and will be tested using ANOVA. Data for each measure and time point will also be presented categorically by severity and tested using Chi-Square or Fisher's exact test.

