4.2.6. Visit 6 (Month 12 or Early Term) +/- 4 days

Subjects will return at Day 360 for their final clinic visit. Vital signs (see section 4.1 for details) and ECGs will be recorded. A physical examination will be performed. Study personnel will weigh returned bottles and count bisacodyl for accountability purposes. Subjects will be queried for any adverse events or changes to their concomitant medications. Subjects will complete the PAC-QOL and PAC-SYM questionnaires. Samples for chemistry, hematology and urinalysis will be repeated as outlined in Section

4.1. Clinically significant laboratory abnormalities present at Visit 6 should be followed until resolved or are considered stable.

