APPENDIX B

Patient Assessment of Constipation – Symptom (PAC-SYM) Questionnaire

Patient Assessment of Constipation-Symptom Questionnaire (PAC-SYM)

This questionnaire asks you about your constipation symptoms in the past two weeks. Answer each question according to your symptoms, as accurately as possible.

Please indicate how severe your symptoms have been during the past two weeks. If you have not had the symptom during the past two weeks, check 0. If the symptom seemed mild, check 1. If the symptom seemed moderate, check 2. If the symptom seemed severe, check 3. If the symptom seemed very severe, check 4. Please be sure to answer every question.

How severe have each of these symptoms been in the last two weeks?	Absent 0	Mild 1	Moderate 2	Severe 3	Very Severe 4
1. discomfort in your abdomen					
2. pain in your abdomen					
3. bloating in your abdomen					
4. stomach cramps					
5. painful bowel movements					
6. rectal burning during or after a bowel movement					
7. rectal bleeding or tearing during or after a bowel movement					
8. incomplete bowel movement, like you didn't "finish"					
9. bowel movements that were too hard					
10. bowel movements that were too small					
11. straining or squeezing to try to pass bowel movements					
12. feeling like you had to pass a bowel movement but you couldn't (false alarm)					

Proprietary information of Janssen Research Foundation
 All rights reserved. 1997.

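### ECG visit comparisons and PAC severity categories are assigned tests with no stated within-subject form, in a one-arm study that measures the same subjects repeatedly (minor)

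*Combined protocol and SAP*

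**What the plan says.** The sole objective (section 2) is "To evaluate the safety of chronic use of BLI400 laxative in constipated adults". The Primary Endpoint entry on the summary sheet begins "Safety will be analyzed through the use of adverse event and ECG data". There is no comparator arm (section 3.1). The procedures table (section 4.3) schedules ECGs at Visits 1, 2 and 6, and the PAC-QOL and PAC-SYM questionnaires at Visits 1 to 6.

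The analysis text on the two outcomes is:

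- **ECG (section 9.3.2):** "The differences in ECG variables between Visit 1 (Baseline), Visit 2 and Visit 6 will be tested using ANOVA". No factor, subject term, covariance or contrast is given.
- **PAC severity categories (section 9.3.3):** "Data for each measure and time point will also be presented categorically by severity and tested using Chi-Square or Fisher's exact test". No comparison is named. Appendix B asks "How severe have each of these symptoms been in the last two weeks" and offers five answers, scored 0 to 4.

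Elsewhere the plan does work within subject. For PAC scores it says "Change from baseline to each visit time point will be presented for each collected measure and will be tested using ANOVA", and for laboratory values "Results of laboratory tests for the change from baseline (Visit 1) and group differences will be tested using ANOVA". The file contains two copies of the protocol with the same wording on these points. It contains no separate SAP text that adds a paired, repeated-measures or mixed-model form.

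**The concern.** One cohort measured repeatedly gives correlated values. A one-way ANOVA with visit as the factor leaves between-subject variance in the error term. Chi-Square and Fisher's exact test on two visits treat the same people as two separate groups. In both cases positive correlation makes the test reject too seldom.

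The ECG sentence lists visits as the things compared, and unlike the laboratory and PAC score sentences it does not mention change from baseline. An analyst could therefore run it as one-way ANOVA. With no control arm, the natural comparison for the PAC categories is each visit against baseline, which is paired.

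In a safety study, what is at stake is how a non-significant result is read. A small real ECG drift could be reported as no significant change because the test was insensitive.

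**Working it through.** **Inputs from the documents.** One arm; 300 subjects (section 9.1, chosen for exposure and not by a power calculation); three ECG visits. The plan gives no alpha, power, SD, correlation or effect size for these tests, so there is no figure of its own to reproduce.

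**Assumptions.** Two-sided 0.05; equal correlation ρ between visits, 0.5 unless varied; complete data unless stated; the shift sizes and category rates shown.

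**1. ECG, size.** With SD 1, the between-visit mean square has expectation 1 − ρ when there is no drift. The one-way error mean square has expectation about 1.

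- The true size is about P(F(2, 598) > F_crit/(1 − ρ)), with F_crit(2, 897) = 3.006.
- At ρ = 0.5 this is P(F > 6.01) = 0.0026. Simulation gives about 0.2% to 0.3%.
- At ρ = 0.3 it is 1.4%, and at ρ = 0.7 about 0.005%.
- A repeated-measures F test stays at about 5%.

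**2. ECG, power for a drift of 0, 0.10, 0.20 SD.**

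- The squared deviations from the mean of 0.10 sum to 0.01 + 0 + 0.01 = 0.02.
- The noncentrality is λ = 300 × 0.02/(1 − 0.5) = 12.
- Repeated-measures F(2, 598), critical value 3.011: power 88%.
- One-way, same λ, effective critical value 6.01: power about 55% to 56%.

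| ρ | One-way | Repeated measures |
|---|---|---|
| 0.3 | 57% | about 75% |
| 0.5 | 55–56% | 88% |
| 0.7 | 54–55% | 98% |
| 0.8 | 53–55% | 99.9% |

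**3. ECG, where the loss ends.** For a sustained shift of 0.30 SD the squared deviations are 0.04 + 0.01 + 0.01 = 0.06, so at ρ = 0.5 λ = 300 × 0.06/0.5 = 36. Power is then above 99% with either test, and at ρ = 0.3 it is still at least 98.8%. The smallest sustained shift with 80% power at ρ = 0.5 is about 0.21 SD one-way and 0.16 SD repeated-measures.

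**4. ECG, with dropout.** A one-way ANOVA would use every available value. With an assumed 300/255/210 values at Visits 1/2/6, missing completely at random, its power for the drift in step 2 is about 45/41/39% at ρ = 0.5/0.7/0.8.

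**5. PAC category, size.** A latent correlation of 0.5 gives a correlation between the two yes/no results of φ ≈ 0.33 at 40% on both visits. The unpaired test overstates the SE by the factor 1/√(1 − φ), so it rejects when the true |z| exceeds 1.96/√(1 − 0.334) = 2.40. The size is 1.6%.

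**6. PAC category, power for 40% to 32%** (φ ≈ 0.32).

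- Unpaired SE = √(0.36 × 0.64 × 2/300) = 0.0392.
- True SE = √{[0.24 + 0.2176 − 2 × 0.321 × √(0.24 × 0.2176)]/300} = 0.0322.
- Chi-Square: Φ[(0.08 − 1.96 × 0.0392)/0.0322] = Φ(0.10) = 54%.
- McNemar: Φ(0.08/0.0322 − 1.96) = Φ(0.53) = 70%.
- At latent correlation 0.7 the pair is about 54% and 81%.
- For 40% to 28% at latent correlation 0.5, the simulated pair is 92% and 96%, so little is lost.

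**The case against.** The strongest reply is that no wrong test has been shown. Repeated-measures ANOVA is an ANOVA, and for three visits in one cohort it is the natural form. The ECG figures for the one-way test therefore measure one reading of the sentence, not a method that the plan imposes. That stands: a reader might infer that the plan specifies an invalid ECG analysis, and the text does not say so.

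The PAC part is conditional too. If the categories were compared between, say, elderly and non-elderly subjects, Chi-Square or Fisher would be valid. The plan uses that split for laboratory data, but nothing attaches it to the PAC categories. What can be said firmly is that the comparison is unnamed, and that the named tests do not suit the most natural one.

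A reader might also restrict the one-way test to an assumed set of completers and find a much larger loss. The documents give no retention figure, and a one-way test is not limited to completers. Visit 6 also serves as the early-termination visit, where "Vital signs (see section 4.1 for details) and ECGs will be recorded", so many who leave early should still have a final ECG.

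Finally, the consequence is limited. The sample size does not rest on these tests, the ECG summaries by visit are unaffected, and PAC lies outside the primary endpoint and the sole objective. All of this stands and sets the weight. It does not remove the gap: the wording leaves the analyst a choice between tests that differ by about 18 to 45 percentage points of power for the small ECG drift above.

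**Conclusion.** The point holds as under-specification, with minor weight. The plan should state a within-subject form for the ECG comparison. For the PAC categories it should state the comparison and use a paired test if that comparison is with baseline.

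The direction of the error needs only positive correlation between visits. Its size rests on the assumed correlations, shifts, category rates and alpha. At n = 300 the ECG loss matters only for mean shifts of about 0.20 SD or less.

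A reader might infer that the study would raise false safety signals or reach a wrong conclusion. The documents do not support that: the error is conservative, and no decision rule depends on these p-values. The harm is confined to over-reading non-significant results.

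The laboratory and PAC change scores are already within-subject. Stating that mean change is tested against zero, and what is meant by group differences, would be helpful clarification but is not part of this point. The adverse-event test between study periods is also left out, because its periods are undefined.

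**What to change.** **ECG (section 9.3.2).** Replace the unqualified ANOVA with a mixed model for repeated measures that has visit as a fixed effect and a subject effect and uses all available visits. Report contrasts of Visit 2 and Visit 6 against Visit 1 with 95% confidence intervals. Classical repeated-measures ANOVA is a poorer choice because it drops subjects who miss a visit.

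**PAC categories (section 9.3.3).** State that the severity categories at each visit are compared with baseline. Replace Chi-Square and Fisher with McNemar's test for two categories, or Stuart-Maxwell or Bowker for more than two, and say how many categories are used.

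**Cost.** A few sentences, made by written amendment with IRB approval as section 12.3 requires. No new data, visits or special software are needed. The one statistical cost is that the paired category tests use only subjects with both the baseline and the later visit, so the number of pairs should be reported at each visit.

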9.3.3. Efficacy Analyses (Patient Reported Outcomes)

Subject constipation symptoms and quality of life indicators will be analyzed using data from the subject-completed PAC-SYM and PAC-QOL instruments. Change from baseline to each visit time point will be presented for each collected measure and will be tested using ANOVA. Data for each measure and time point will also be presented categorically by severity and tested using Chi-Square or Fisher's exact test.

9.4. Study Populations

The following populations have been defined for data analyses.

9.4.1. Intention-to-Treat (ITT) Population

This population includes all enrolled subjects that were dispensed study medication.

9.4.1. Modified Intention-to-Treat (mITT) Population

This population consists of all enrolled subjects that took at least one dose of study medication. This population will be utilized for all safety analyses.

9.4.2. **Per-Protocol Population**

The per-protocol (PP) population will consist of all subjects in the mITT population who have not violated study entry criteria and have not deviated significantly from the protocol during the course of the study. Any analyses from this population will be considered as supportive to the ITT and mITT analyses. Reasons for exclusion from the PP population will be defined in the clinical study report.

10. **DRUG INVENTORY AND DISPOSITION**

At the conclusion of the study, all drug materials will be accounted for. Federal law requires that, at the conclusion of the study, all drug materials must be returned to the study sponsor or destroyed according to local regulations.

11. **STUDY MONITORING**

A Braintree Laboratories Study Monitor or qualified designee will visit the study center prior to the commencement of the study and periodically during the course of the study in accordance with federal guidelines governing the sponsorship of studies.

12. **DOCUMENTS AND NOTIFICATIONS**

12.1. **Informed Consent**

Written informed consent will be obtained from the subjects by the Investigator and will be kept on file at the study center. Documentation of the consent process should be noted in the study source documents.

12.2. **Institutional Review Board**

Peer review and approval of the protocol by an appropriate Institutional Review Board is required prior to commencement of enrollment. Amendments to the approved protocol must also be submitted to the Institutional Review Board and approved prior to their implementation.

12.3. Amendments to the Protocol

The Investigator and Braintree Laboratories will discuss any amendments to the study protocol. If an agreement is reached regarding the need for the amendment, it will be produced in writing by Braintree Laboratories and will be made a formal part of the protocol only after approval by an Institutional Review Board.

12.4. Data Records

Site personnel will be required to enter study data into electronic case report forms (eCRFs) provided by Braintree Laboratories. Subject medical records will be reviewed to verify study data points, including potential adverse events, and to ensure correctness and consistency with the CRF entries. The Investigator should retain copies of paper and electronic data, patient consent/assent forms, and other study documents for a period of two years following the date of approval of a New Drug Application or supplement for BLI400 laxative, or, if the application is not approved, for two years after the drug investigation program is discontinued. These records will be made available at reasonable times for inspection and copying if requested by a properly authorized employee of Braintree Laboratories or the Department of Health and Human Services in accordance with federal regulations.

13. PUBLICATION AND AGREEMENT

The results of this study will be published if mutually agreed by Braintree Laboratories and the Investigator and at a mutually agreed upon date. Investigator agrees to submit to Braintree Laboratories, within sixty (60) days of the proposed submission date, any proposed publication or presentation for prior review. Braintree Laboratories will, within thirty (30) days after receipt, advise if there is any proprietary or patentable information, which should not be disclosed at the present time. Investigator shall not release any such proposed publication or presentation, if so notified by Braintree Laboratories.

Braintree Laboratories, Inc.
Protocol Number BLI400-303

Confidential

APPENDIX A

Patient Assessment of Constipation – Quality of Life (PAC-QOL) Questionnaire

PAC-QOL ©					
PATIENT ASSESSMENT OF CONSTIPATION					
The following questions are designed to measure the impact constipation has had on your daily life over the past 2 weeks. For each question, please check one box.					
The following questions ask about your symptoms related to constipation. During the past 2 weeks, to what extent or intensity have you...	Not at all 0	A little bit 1	Moderately 2	Quite a bit 3	Extremely 4
1. felt bloated to the point of bursting?					
2. felt heavy because of your constipation?					
The next few questions ask about how constipation affects your daily life . During the past 2 weeks, how much of the time have you...	None of the time 0	A little of the time 1	Some of the time 2	Most of the time 3	All of the time 4
3. felt any physical discomfort?					
4. felt the need to have a bowel movement but not been able to?					
5. been embarrassed to be with other people?					
6. been eating less and less because of not being able to have bowel movements?					

PAC-QOL

Copyright © 1997. Janssen Research Foundation. All rights reserved.

Patient Assessment of Constipation – Quality of Life (PAC-QOL) Questionnaire

The next few questions ask about how constipation affects your daily life . During the past 2 weeks, to what extent or intensity have you...	Not at all 0	A little bit 1	Moderately 2	Quite a bit 3	Extremely 4
7. had to be careful about what you eat?					
8. had a decreased appetite?					
9. been worried about not being able to choose what you eat (for example, at a friend's house)?					
10. been embarrassed about staying in the bathroom for so long when you were away from home?					
11. been embarrassed about having to go to the bathroom so often when you were away from home?					
12. been worried about having to change your daily routine (for example, traveling, being away from home)?					
The next few questions ask about your feelings related to constipation. During the past 2 weeks, how much of the time have you...	None of the time 0	A little of the time 1	Some of the time 2	Most of the time 3	All of the time 4
13. felt irritable because of your condition?					
14. been upset by your condition?					
15. felt obsessed by your condition?					
16. felt stressed by your condition?					
17. felt less self-confident because of your condition?					
18. felt in control of your situation?					

PAC-QOL

Copyright © 1997. Janssen Research Foundation. All rights reserved.

Patient Assessment of Constipation – Quality of Life (PAC-QOL) Questionnaire

The next questions ask about your feelings related to constipation. During the past 2 weeks, to what extent or intensity have you...	Not at all 0	A little bit 1	Moderately 2	Quite a bit 3	Extremely 4
19. been worried about not knowing when you are going to be able to have a bowel movement?					
20. been worried about not being able to have a bowel movement?					
21. been more and more bothered by not being able to have a bowel movement?					
The next questions ask about your life with constipation . During the past 2 weeks, how much of the time have you...	None of the time 0	A little of the time 1	Some of the time 2	Most of the time 3	All of the time 4
22. been worried that your condition will get worse?					
23. felt that your body was not working properly?					
24. had fewer bowel movements than you would like?					
The next questions ask about your degree of satisfaction related to constipation. During the past 2 weeks, to what extent or intensity have you been...	Not at all 0	A little bit 1	Moderately 2	Quite a bit 3	Extremely 4
25. satisfied with how often you have a bowel movement?					
26. satisfied with the regularity of your bowel movements?					
27. satisfied with the time it takes for food to pass through the intestines?					
28. satisfied with your treatment?					

PAC-QOL

Copyright © 1997. Janssen Research Foundation. All rights reserved.

